4.13.3 Cough VAS

A summary by treatment group (different doses of AZD1402, pooled AZD1402 and placebo) in terms of absolute values at baseline, average over the treatment period, and change from baseline average over the treatment period, will be presented for cough VAS. Information from the VAS assessments will also be listed.

For cough VAS the average is defined as:

(sum of values in treatment period)/(number of e-Diary sessions completed during period)

The average over the treatment will be calculated as the average of all assessments measurements for a given subject during the treatment period.

All the efficacy variables will be presented in listings.

4.14 Exploratory CCI Variables (Part 2)

All the exploratory analysis will be presented based on FAS.

Statistical Analysis Plan

4.14.1 CCI

CCI

CCI

4.14.2 CCI

CCI

4.15 Pharmacokinetics

4.15.1 Pharmacokinetic Concentrations

The PK parameters will be summarised and plotted separately for Part 1 and for Part 2 by dose level, nominal timepoints (PK Day) and for ADA status. Pharmacokinetic serum concentration data for AZD1402, will be listed by dose level (treatment) and subject. Listings will include actual sampling times relative to dose administration. Serum concentrations below the lower limit of quantification (LLOQ) will be presented as BLQ in the listings. Serum concentrations for AZD1402 will be summarised by dose level, and nominal timepoint (PK Day).

Summary statistics for the PK serum concentrations will be presented separately for Part 1 and for Part 2 by dose level, nominal timepoints (PK Day) and for ADA status and will include number of observations, number of observations below the LLOQ, geometric mean, Geometric CV% (calculated as: $\text{GeoCV\%} = \text{SQRT}(e^s - 1) * 100$; where s is the SD of the log transformed values), geometric mean, arithmetic mean, arithmetic SD, median, minimum, and maximum. Any values that are not reportable or where no sample is available will be excluded from the summary tables. Three observations $>$ LLOQ are required as a minimum for a serum concentration to be summarised. Where there are only 2 observations $>$ LLOQ, these are presented as minimum and maximum and the other summary statistics are not calculated.

The following rules will be followed with regards to the number of decimal places and presentation of data in the tables and listings of concentration data:

- Source data shall be used in all derived PK concentrations without prior rounding.
- The mean, SD, geometric mean and median will be tabulated to 1 more significant digit compared to the source data, but with a maximum of 4 significant digits.
- Minimum and maximum values will be tabulated to the same precision as the source data, but with a maximum of 4 significant digits.

- Geometric CV% will be presented to 1 decimal place.

To visualise the comparison between dose levels the following descriptive PK graphs will be generated for each part:

- Geometric Mean (\pm gSD) AZD1402 serum concentration versus time by dose (linear scale and semi-log linear scale) presented for all doses overlaid on the same plot for a given PK Day (Day 1, Day 28). A different graph will be created for each ADA status.
- Geometric Mean (\pm gSD) AZD1402 serum concentration-time data (linear scale and semi-log linear scale) presented for PK Days 1 and 28 overlaid on the same plot for a given dose level. A different graph will be created for each ADA status.
- Individual Ctrough of AZD1402 will be plotted versus study day (linear scale and semi-log linear scale) for each dose level and all PK days (Day 1 to Day 56 for Part 1 and Day 1 to Day 39 for Part 2). A different graph will be created for each ADA status.
- Geometric mean (\pm gSD) AZD1402 Ctrough versus study day (linear scale and semi-log linear scale) will be presented for all study days (Day 1 to Day 56 for Part 1 and Day 1 to Day 39 for Part 2) and by dose overlaid on the same plot. A different graph will be created for each ADA status.
- Individual serum concentrations of AZD1402 versus actual time by dose will be plotted for each subject in linear and semi-log linear scale separately for Day 1 and Day 28.
- Individual serum concentrations of AZD1402 versus actual time by dose will be plotted for each Subject in linear and semi-log linear scale overlaid on the same figure for Day 1 and Day 28 (dose levels will be displayed separately).
- Box plot of Ctrough over time by ADA category.

4.15.2 Handling of Values Below the Limit of Quantification for Summarising and Presentation of Concentration Data

Individual concentrations below the LLOQ of the bioanalytical assay will be reported as BLQ in the listings with the LLOQ defined in the footnotes of the relevant TFLs. Individual serum concentrations that are Not Reportable will be reported as NR and those that are missing will be reported as NS (No Sample) in the listings.

Serum concentrations that are BLQ, NR, or NS will be handled as follows for the provision of descriptive statistics:

- Any values report as NR or NS will be excluded from the summary tables and figures.
- At a time point where less than or equal to 50% of the values are BLQ, all BLQ values will be set to the LLOQ, and all descriptive statistics will be calculated accordingly.
- At a time point where more than half (but not all) of the values are BLQ, the geometric mean, Geometric mean/gD, Geometric mean * gSD and GeoCV% will be set to Not Determined (ND). The maximum value will be reported from the individual data, and the minimum and median will be set to BLQ.
- If all values are BLQ at a time point, no descriptive statistics will be calculated for that time point. The arithmetic mean, geometric mean, minimum, median, and maximum will be

reported as BLQ and the SD, GeoCV% and geometric mean / gSD and geometric mean * gSD as Not Applicable (NA).

- The number of BLQ values (n below LLOQ) will be reported for each time point.

Three observations > LLOQ are required as a minimum for a serum concentration to be summarised. If there are only 2 observations > LLOQ they are presented as minimum and maximum and the other summary statistics presented as NA.

Pharmacokinetic concentration and parameter data for subjects excluded from the PK set will be included in the data listings, but not in the descriptive or inferential statistics or in mean figures or combined individual figures.

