CL/F	Apparent total body clearance of drug from serum after extravascular administration
Vz/F	Volume of distribution (apparent) at steady state following extravascular administration (based on terminal phase)
Dose normalised AUC τ	Area under the serum concentration-time curve in the dosing interval τ divided by the dose administered
Dose normalised Cmax	Maximum observed serum (peak) drug concentration divided by the dose administered
Dose normalised AUClast	Area under the serum concentration-time curve from zero to the last quantifiable concentration divided by the dose delivered in mg
tlast	Time of last observed (quantifiable) serum concentration
Rac AUC	Accumulation ratio for AUC τ
Rac Cmax	Accumulation ratio for Cmax

The following diagnostic parameters for PK analysis will be provided:

λz lower	Lower (earlier) t used for λz determination
λz upper	Upper (later) t used for λz determination
λzN	Number of data points used for λz determination
Rsq	Statistical measure of fit for the regression used for λz determination
Rsq adj	Statistical measure of fit for the regression used for λz determination adjusted for the number of used data points (n obs)
λz span ratio	Time period over which λz was determined as a ration of $t_{1/2\lambda z}$

Additional PK parameters may be determined where appropriate.

Serum concentrations will be listed and summarised by treatment and PK day using appropriate descriptive statistics. Where possible, the following descriptive statistics will be presented: n, geometric mean, geometric coefficient of variation, geometric mean +geometric standard deviation, geometric mean -geometric standard deviation, arithmetic mean, arithmetic SD, median, minimum and maximum based on the PK analysis set. Serum concentrations that are BLQ will be handled as described in the SAP.

Combined individual serum concentration per dose level and PK day (spaghetti plots) will be presented in linear and semi-logarithmic scale with separate plots for each dose level and PK day. Figures for the geometric mean concentration-time data will be presented for all doses overlaid on the same plot for a given PK day, in both a linear and semi-logarithmic scale.

Figures for the geometric mean concentration-time data will also be presented for PK Days 1 and 28 overlaid on the same plot for a given dose level, in both a linear and semi-logarithmic scale.

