All confidence intervals (CIs) will be 2-sided 95% CIs, unless stated otherwise, and presented to one more decimal place than the raw data recorded in the database. If a model is used to estimate the treatment difference, the corresponding CI according to the model will be presented. Otherwise, the unadjusted CI will be used. Nominal p-values may also be presented. Care should be taken when interpreting CIs and p-values since no correction for multiple testing is done for the endpoints.

P-values greater than or equal to 0.001, in general, will be presented to 3 decimal places. P-values less than 0.001 will be presented as “<0.001”.

Descriptive statistics for calculated PK parameters and FeNO will include: n , mean, SD, geometric mean, geometric coefficient of variation (GeoCV%), median, minimum and maximum values.

The GeoCV% will be calculated as $SQRT(es^2-1)*100$ where s is the SD of the log-transformed values.

Daylight saving dates will be considered in the calculation of the absolute scheduled and actual times and in the duration when this is based on times. Therefore, if any daylight saving change occurs during the study development, this will impact the description of the blood sample collections, the calculation of the PK parameters and any AE duration in case the time is included in the calculation of the duration.

Statistical Analysis Plan

All other requirements and specifications for programming and presentation of TFLs will be specified in the TFL shells document.

The following rules will be applied for any repeated safety assessments:

- For repeated assessments at any timepoint before first IP administration (including screening values and baseline): the latest assessment obtained per timepoint will be used in the calculation of descriptive statistics.
- For repeated assessments at any timepoint after first IP (including Follow-up visit): the first (non-missing) value after dosing will be used in the calculation descriptive statistics.

The AM and PM assessments will be combined into a daily assessment according to the following formula:

Let assessment (Day i) = (PM assessment (Day i) + AM assessment Day (i+1)) / 2

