- AUCs (including AUClast and AUC τ) will be calculated using the linear trapezoidal method when concentrations are increasing and the logarithmic trapezoidal method when concentrations are decreasing (linear up log down). The minimum requirement for the

Statistical Analysis Plan

calculation of AUC will be the inclusion of at least 3 consecutive serum concentrations above the LLOQ.

- If the concentration at the time of dosing is missing, then this will be set to 0.
- Data exclusions from analysis should be avoided. However, in clear cases of technical issues, such as documented sample mix up, bioanalytical error or mis-dosing, individual or subject level data may be excluded from summaries or summarised separately. Data exclusions will be agreed with the AstraZeneca Clinical Pharmacology Scientist and discussed in the CSR.
- Pharmacokinetic parameters associated with positive pre-dose value(s) of greater than 5% Cmax for the first dose may be excluded from the summary statistics of PK tables and statistical analysis at the discretion of the pharmacokineticist.

Pharmacokinetic parameters will be listed by subject and summarised by AZD1402 dose and study Part. Descriptive statistics for calculated PK parameters will include: n, mean, SD, geometric mean, GeoCV%, median, minimum and maximum values. For tmax, only median, minimum, and maximum values will be presented. No descriptive statistics will be determined when fewer than 3 individual PK parameters are available.

The following rules will be followed with regards to the number of decimal places and presentation of data in the tables and listings for PK parameters:

- Individual PK parameters will be presented to 4 significant digits, with the exception of tmax, which will be presented to 2 decimal places.
- Parameters derived directly from source data (eg, Cmax₀) shall be reported with the same precision as the source data (if this is not 4 significant digits).
- The mean, geometric mean, median, and SD values will be reported to 4 significant digits, all other descriptive statistics will be reported to 3 significant digits.
- For tmax, the minimum and maximum will be presented to 2 decimal places and all other descriptive statistics will be presented to 3 decimal places.
- Estimates and CIs in the form of percentages will be presented to 2 decimal places.

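### As printed, SAP 4.15.1 leaves s unsquared in the geometric CV for PK serum concentrations, contradicting SAP 4.2 and misstating that one descriptive statistic

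*SAP*

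**What the plan says.** The SAP defines the geometric CV twice.

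- **SAP 4.2** introduces the statistic for two kinds of data: "Descriptive statistics for calculated PK parameters and FeNO will include: n , mean, SD, geometric mean, geometric coefficient of variation (GeoCV%), median, minimum and maximum values". It then gives the formula: "The GeoCV% will be calculated as $SQRT(es^2-1)*100$ where s is the SD of the log-transformed values". The superscript has been flattened in the text available to us, but s is squared.
- **SAP 4.15.1** sets out the summaries of AZD1402 serum concentrations by study part, dose level, nominal time and ADA status. Its formula is the square root of ("e^s - 1) * 100$; where s is the SD of the log transformed values"). Here s is not squared.

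SAP 4.15.3 asks for the same statistic for PK parameters and gives no formula: "Descriptive statistics for calculated PK parameters will include: n, mean, SD, geometric mean, GeoCV%, median, minimum and maximum values". The definition in 4.2 therefore applies to them. Protocol 9.4.4.1 also requires the geometric CV for serum concentrations, again without a formula: "n, geometric mean, geometric coefficient of variation, geometric mean +geometric standard deviation".

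The list of statistics in SAP 4.15.1 names the geometric mean twice and does not name the geometric mean with geometric SD limits.

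**The concern.** A log-normal variable has a coefficient of variation that depends on the variance of the logs, so the exponent must hold s squared. With s alone, the expression would be right only if s stood for the variance, and 4.15.1 says that it is the SD. Section 4.15.1 is the specific section for concentration tables, so a programmer could reasonably follow it over the general section.

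The stake is a wrong descriptive figure, repeated over every dose, time point and ADA group in those tables and not comparable with the PK parameter tables in the same report. Trough values show the problem most clearly. SAP 3.2.3 lists Ctrough as a PK parameter, and the same pre-dose samples also appear as serum concentrations by nominal time. If both are tabulated, the same troughs could carry CVs computed by two different formulas.

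**Working it through.** The plan states no numerical geometric CV, so there is no figure of its own to reproduce. The check compares the two formulas.

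**Inputs.** The two formulas come from SAP 4.2 and 4.15.1. The values of s are assumptions, shown over a range.

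**Which form is right.** If log X is normal with SD s, then CV = sqrt(exp(s^2) - 1). For a CV of 30%, s = sqrt(ln(1 + 0.30^2)) = sqrt(ln 1.09) = 0.2936. A simulation of 4 million log-normal values with that s gave an arithmetic CV of 0.2999, which confirms the squared form.

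**Reading 4.2.** Taken literally, the flattened text would be e times s^2, minus 1. At s = 0.2936 that is -0.766, which has no square root. The exponent reading, exp(s^2), is the sensible one.

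**Where the two agree.** They are equal only when s = s^2, that is at s = 0 or s = 1. Between 0 and 1, s exceeds s^2 and the 4.15.1 form is too large. Above 1 it is too small.

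**Size by log-scale SD.** At s = 0.3, for example, sqrt(exp(0.3) - 1) = 59.1%, against sqrt(exp(0.09) - 1) = 30.7%.

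| s (assumed) | 4.15.1 as printed | 4.2 (correct) |
|---|---|---|
| 0.2 | 47.1% | 20.2% |
| 0.3 | 59.1% | 30.7% |
| 0.5 | 80.5% | 53.3% |
| 0.7 | 100.7% | 79.5% |
| 1.0 | 131.1% | 131.1% |
| 1.5 | 186.6% | 291.3% |

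**Size by true CV.** Using s = sqrt(ln(1 + CV^2)):

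| True CV (assumed) | 4.15.1 as printed | Ratio |
|---|---|---|
| 10% | 32.4% | 3.24 |
| 30% | 58.4% | 1.95 |
| 50% | 77.7% | 1.55 |
| 100% | 114.0% | 1.14 |
| 200% | 159.9% | 0.80 |
| 300% | 188.7% | 0.63 |

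**The case against.** The strongest objection is that the missing square may not be in the SAP at all. The correct formula has a superscript within a superscript, which text extraction easily loses, and the formula in 4.2 is visibly damaged in the same way. If 4.2 lost one level, 4.15.1 may have lost the inner 2. This stands: the text alone cannot separate a drafting error from a lost character, so the point depends on a look at the source PDF.

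A second objection is that harm is unlikely. The standard form is already in the general section, SAP 4.2 leaves further programming detail to the table shells, and SAP 4.1 requires independent checking of outputs. This lowers the risk. It does not remove the contradiction, because a checker working from 4.15.1 would reproduce the same number.

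A reader might also infer that PK variability in general would be misreported, or that it would be about doubled. The documents support neither. Cmax, AUC and the other PK parameters follow 4.2, as does FeNO. A doubling is what happens near a true CV of 30%, and that value is not in the documents. Nor do they say that this CV feeds later dose or exposure modelling.

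The repeated geometric mean in the 4.15.1 list is largely clerical. SAP 4.15.2 already has handling rules for the geometric mean divided by and multiplied by the geometric SD, so those statistics are evidently planned.

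**Conclusion.** On the text as it reads, the two SAP formulas conflict and the one in 4.15.1 is wrong for log-normal data. The consequence is confined to the geometric CV in the serum-concentration tables. That figure would be too high for s below 1 (a true CV below about 131%) and too low above it, by the amounts tabulated, if the tables are programmed from 4.15.1. How far any actual table would be off cannot be said, because no AZD1402 variability is given.

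The statistic is descriptive. It does not enter the FEV1 model in SAP 4.11 or the sample size in SAP 4.19. The Part 1 exposure stopping rule in Protocol 4.4.1 uses an individual participant's Cmax or AUC, so it is untouched as well.

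The conclusion rests on two assumptions: that the square is absent from the source PDF, and that 4.2 means exp(s^2).

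**What to change.** Check SAP 4.15.1 in the source PDF. If s is squared there, the formula needs no change. If it is not, write GeoCV% = 100 x sqrt(exp(s^2) - 1), or replace the formula with a reference to SAP 4.2, so that one definition serves all tables. Confirm that the table shells and programs use the same form.

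As a minor tidy-up, replace the second geometric mean in the 4.15.1 list with geometric mean / gSD and geometric mean x gSD, to match SAP 4.15.2. Protocol 9.4.4.1 words these limits as plus and minus the geometric SD, so the SAP should state that it uses the multiplicative form.

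The cost is a one-line correction to the SAP, plus one line for the list. No data collection or design element changes.

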4.15.3 Pharmacokinetic Parameters

Pharmacokinetic parameters will be calculated by non-compartmental analysis methods from the concentration-time data using Phoenix® WinNonlin® (Version 8.1) or higher following these guidelines:

- Concentration data will be used as supplied by the analytical laboratory for PK analysis. The units of concentration and resulting PK parameters, with the amount and concentration units, will be presented as they are received from the analytical laboratory.
- Cmax and tmax will be derived directly from the serum concentration-time profiles. For multiples peaks the highest post-dose concentration will be reported as Cmax. In the case that the multiple peaks are of equal magnitude, the earliest tmax will be reported.
- Serum concentrations which are BLQ from the time of pre-dose sampling ($t = 0$) up to the time of first quantifiable concentration will be set to a value of zero. After the first quantifiable concentration, any BLQ serum concentrations will be set to missing for all concentration profiles.
- Where 2 or more consecutive concentrations are BLQ at the end of a profile, the profile will be deemed to have terminated and therefore any further quantifiable concentrations will be set to missing for the calculation of the PK parameters unless there is a scientific rational not to do so, which will be documented in the CSR.
- Any embedded BLQ value (between 2 quantifiable concentrations) will be set to missing for the purposes of PK analysis.
- If an entire concentration-time profile is BLQ, the profile will be excluded from the PK analysis.
- Terminal elimination half-life, calculated as $(\ln 2)/\lambda_z$, will be estimated by log-linear LS regression of the terminal part of the concentration-time curve. The start of the terminal elimination phase for each subject will be defined by visual inspection and will be the first point at which there is no systematic deviation from the log-linear decline in serum concentrations. A minimum of 3 data points following Cmax and including the last measurable concentration will be used in calculating λ_z . The duration of time over which λ_z should, where possible, span 3 half-lives. The adjusted correlation coefficient (Rsq adj) should be ≥ 0.8 .
- AUCs (including AUClast and AUC τ) will be calculated using the linear trapezoidal method when concentrations are increasing and the logarithmic trapezoidal method when concentrations are decreasing (linear up log down). The minimum requirement for the

Statistical Analysis Plan

calculation of AUC will be the inclusion of at least 3 consecutive serum concentrations above the LLOQ.

- If the concentration at the time of dosing is missing, then this will be set to 0.
- Data exclusions from analysis should be avoided. However, in clear cases of technical issues, such as documented sample mix up, bioanalytical error or mis-dosing, individual or subject level data may be excluded from summaries or summarised separately. Data exclusions will be agreed with the AstraZeneca Clinical Pharmacology Scientist and discussed in the CSR.
- Pharmacokinetic parameters associated with positive pre-dose value(s) of greater than 5% Cmax for the first dose may be excluded from the summary statistics of PK tables and statistical analysis at the discretion of the pharmacokineticist.

Pharmacokinetic parameters will be listed by subject and summarised by AZD1402 dose and study Part. Descriptive statistics for calculated PK parameters will include: n, mean, SD, geometric mean, GeoCV%, median, minimum and maximum values. For tmax, only median, minimum, and maximum values will be presented. No descriptive statistics will be determined when fewer than 3 individual PK parameters are available.

The following rules will be followed with regards to the number of decimal places and presentation of data in the tables and listings for PK parameters:

- Individual PK parameters will be presented to 4 significant digits, with the exception of tmax, which will be presented to 2 decimal places.
- Parameters derived directly from source data (eg, Cmax₀) shall be reported with the same precision as the source data (if this is not 4 significant digits).
- The mean, geometric mean, median, and SD values will be reported to 4 significant digits, all other descriptive statistics will be reported to 3 significant digits.
- For tmax, the minimum and maximum will be presented to 2 decimal places and all other descriptive statistics will be presented to 3 decimal places.
- Estimates and CIs in the form of percentages will be presented to 2 decimal places.

